14.3.1 Displays of Adverse Events

Overall Summary of Adverse Events Table 25:

	HEV (N =	/-239 = xx)	Plac (N =	cebo = xx)	All Subjects (N = xx)				
Subjects ^a with	n	%	n	%	n	%			
At least one local solicited adverse event	x	x	x	x	x	x			
At least one systemic solicited adverse event	x	x	x	x	x	x			
At least one unsolicited adverse event	x	x	х	x	x	х			
At least one related unsolicited adverse event	x	x	х	x	x	x			
Mild (Grade 1)	x	x	x	x	x	x			
Moderate (Grade 2)	х	х	x	х	х	x			
Severe (Grade 3)	x	x	x	x	x	x			
At least one severe (Grade 3) unsolicited adverse event	x	x	x	x	x	x			
Related	х	х	x	х	х	х			
Not related	x	x	x	x	x	x			
At least one clinical safety laboratory adverse event	x	x	x	x	x	x			
At least one serious adverse event ^b	x	x	x	x	x	x			
At least one related, serious adverse event	x	x	x	x	x	x			
At least one adverse event leading to early termination ^c	х	x	x	x	x	x			

N = Number of subjects in the Safety Population

^a Subjects are counted once for each category regardless of the number of events.
 ^b A listing of Serious Adverse Events is included in Table 43.

^c As reported on the Adverse Event eCRF.

Table 26:Adverse Events Occurring in 5% of Subjects in Any Treatment Group by MedDRA
System Organ Class and Preferred Term, and Treatment Group - Safety Population

Preferred Term	MedDRA System Organ Class		HEV-239 (N=X))		Placebo (N=X)		All Subjects (N=X)			
		n	%	Events	n	% Events		n	%	Events	
Serious Adverse Events											
All	All	х	х	х	х	х	х	х	х	х	
PT1	SOC1	х	х	х	х	х	х	х	х	х	
Etc.	Etc.										
Other (Non-serious) Adverse	e Events										
All	All	х	х	х	х	х	х	х	х	х	
PT1	SOC1	х	х	х	х	х	х	х	х	х	
Etc	Etc										

N = number of subjects in the Safety Population (number of subjects at risk).

n= number of subjects reporting event.

Events= total frequency of events reported.

14.3.1.1 Solicited Adverse Events

Table 27:Number and Percentage of Subjects Experiencing Solicited Events with 95% Confidence Intervals by Symptom, Dose, and
Treatment Group

		Post HE (N	Dose 1 V-239 V=X)		Post Dose 1 Placebo (N=X)			Post Dose 2 HEV-239 (N=X)			Post Dose 2 Placebo (N=X)			Post Dose 3 HEV-239 (N=X)			Post Dose 3 Placebo (N=X)			Post Any Dose HEV-239 (N=X)			Post Any Dose Placebo (N=X)		
Symptom	n	%	95% CI	n	%	95% CI	n	%	95% CI	n	%	95% CI	n	%	95% CI	n	%	95% CI	n	%	95% CI	n	%	95% CI	
Any Symptom	х	xx	x.x, x.x	x	xx	x.x, x.x	x	xx	x.x, x.x	x	xx	x.x, x.x	x	xx	x.x, x.x	x	xx	x.x, x.x	х	xx	x.x, x.x	x	xx	x.x, x.x	
Any Systemic Symptom																									
Arthralgia																									
Fever																									
Feverishness																									
Fatigue																									
Headache																									
Malaise																									
Myalgia																									
Nausea																									
Vomiting																									
Any Local Symptom																									
Ecchymosis Severity																									
Ecchymosis Measurement																									
Erythema Measurement																									
Induration/Swelling Severity																									
Induration/Swelling Measurement																									
Pain																									
Pruritus																									
Tenderness																									

Note: N=Number of subjects in the Safety Population
]	Post 1 HEV (N:	Dose 1 /-239 =X)]	Post Pla (N	Dose 1 cebo =X)]	Post HEV (N	Dose 2 V-239 =X)]	Post Pla (N	Dose 2 cebo =X)]	Post HE (N	Dose 3 V-239 =X)]	Post 1 Pla (N	Dose 3 cebo =X)	P	ost A HEV (N	ny Dose V-239 =X)	Po	ost Ai Pla (N [:]	ny Dose cebo =X)
Symptom	Severity	n	%	95% CI	n	%	95% CI	n	%	95% CI	n	%	95% CI	n	%	95% CI	n	%	95% CI	n	%	95% CI	n	%	95% CI
Any Symptom	None	x	xx	x.x, x.x	х	xx	x.x, x.x	x	xx	x.x, x.x	x	xx	x.x, x.x	х	xx	x.x, x.x	х	xx	x.x, x.x	х	xx	x.x, x.x	х	xx	x.x, x.x
	Mild																								
	Moderate																								
	Severe																								
Systemic Symptoms																									
Any Systemic Symptom	None	x	xx	x.x, x.x	x	xx	x.x, x.x	x	xx	x.x, x.x	x	xx	x.x, x.x	x	xx	x.x, x.x	x	xx	x.x, x.x	x	xx	x.x, x.x	х	xx	x.x, x.x
	Mild																								
	Moderate																								
	Severe																								
Arthralgia	None																								
	Mild																								
	Moderate																								
	Severe																								
Fever	None																								
	Mild																								
	Moderate																								
	Severe																								
Feverishness	None																								
	Mild																								
	Moderate																								
	Severe																								
Fatigue	None																								
	Mild																								

Table 28: Number and Percentage of Subjects Experiencing Solicited Events by Symptom, Maximum Severity, Dose, and Treatment Group

Table 28: Number and Percentage of Subjects Experiencing Solicited Events by Symptom, Maximum Severity, Dose, and Treatment Group
(continued)

]	Post HE (N	Dose 1 V-239 =X)]	Post I Pla (N	Dose 1 cebo =X)	I	Post I HEV (N	Dose 2 V-239 =X)		Post Pla (N	Dose 2 cebo =X)]	Post HE (N	Dose 3 V-239 (=X)		Post Pla (N	Dose 3 cebo =X)	Р	ost A HEV (N	ny Dose V-239 =X)	Po	ost A Pla (N=	ny Dose cebo =X)
Symptom	Severity	n	%	95% CI	n	%	95% CI	n	%	95% CI	n	%	95% CI	n	%	95% CI	n	%	95% CI	n	%	95% CI	n	%	95% CI
	Moderate																								
	Severe																								
Headache	None																								
	Mild																								
	Moderate																								
	Severe																								
Malaise	None																								
	Mild																								
	Moderate																								
	Severe																								
Myalgia	None																								
	Mild																								
	Moderate																								
	Severe																								
Nausea	None																								
	Mild																								
	Moderate																								
	Severe																								
Vomiting	None																								
	Mild																								
	Moderate																								
	Severe																								
Local Symptoms	•			•				•	•				•		•	•	•					•	•		

Table 28: Number and Percentage of Subjects Experiencing Solicited Events by Symptom, Maximum Severity, Dose, and Treatment Group
(continued)

]	Post i HEV (N	Dose 1 V-239 =X)]	Post Pla (N	t Dose 1 lacebo N=X) 9 95% CI n		Post 1 HEV (N	Dose 2 V-239 =X)		Post Pla (N	Dose 2 cebo =X)		Post HEV (N	Dose 3 V-239 =X)]	Post 1 Pla (N:	Dose 3 cebo =X)	Po	ost A HEV (N:	ny Dose /-239 =X)	Po	st Ai Pla (N:	ny Dose cebo =X)
Symptom	Severity	n	%	95% CI	n	%	95% CI	95% CI n % 9 x.x, x.x x xx x		95% CI	n	%	95% CI	n	%	95% CI	n	%	95% CI	n	%	95% CI	n	%	95% CI
Any Local Symptom	None	x	xx	x.x, x.x	х	xx	x.x, x.x	x	xx	x.x, x.x	x	xx	x.x, x.x	x	xx	x.x, x.x	x	xx	x.x, x.x	x	xx	x.x, x.x	x	xx	x.x, x.x
	Mild																								
	Moderate																								
	Severe																								
Ecchymosis Severity	None																								
	Mild																								
	Moderate																								
	Severe																								
Ecchymosis Measurement	None																								
	Mild																								
	Moderate																								
	Severe																								
Erythema Measurement	None																								
	Mild																								
	Moderate																								
	Severe																								
Induration/Swelling Severity	None																								
	Mild																								
	Moderate																								
	Severe																								
Induration/Swelling Measurement	None																								

Table 28: Number and Percentage of Subjects Experiencing Solicited Events by Symptom, Maximum Severity, Dose, and Treatment Group
(continued)Post Dose 1Post Dose 1Post Dose 1Post Dose 2Post Dose 2Post Dose 3Post Dose 3Post Any DosePost Any DoseHEV-239PlaceboHEV-239Placebo(N=X)(N=X)(N=X)(N=X)(N=X)(N=X)(N=X)(N=X)

			HEV (N	V-239 =X)		Pla (N	cebo =X)		HEY (N	V-239 =X)		Pla (N	icebo =X)		HEY (N	V-239 (=X)		Pla (N	cebo =X)		HE (N	V-239 =X)		Pla (N	cebo =X)
Symptom	Severity	n	%	95% CI	n	%	95% CI	n	%	95% CI	n	%	95% CI	n	%	95% CI	n	%	95% CI	n	%	95% CI	n	%	95% CI
	Mild																								
	Moderate																								
	Severe																								
Pain	None																								
	Mild																								
	Moderate																								
	Severe																								
Pruritus	None																								
	Mild																								
	Moderate																								
	Severe																								
Tenderness	None																								
	Mild																								
	Moderate																								
	Severe												1											1	

 Severe
 Severe

 Note: N = Number of subjects in the Safety Population who received the specified dose. Severity is the maximum severity reported over all solicited symptoms post dosing for each subject.

		Pre	Dose	Post	-Dose	Da	y 1	Da	y 2	Da	iy 3	Da	y 4	Da	ny 5	Da	iy 6	Da	y 7	Day	y 8 +
Symptom	Severity	n	%	n	%	n	%	n	%	n	%	n	%	n	%	n	%	n	%	n	%
Any Symptom	None	х	XX	x	XX	х	XX	х	XX	х	XX	х	XX	х	XX	x	XX	х	XX	х	XX
	Mild																				
	Moderate																				
	Severe																				
	Not Reported																				
Systemic Symptoms																					
Any Systemic Symptom	None	х	XX	х	xx	х	xx	х	XX	х	xx	х	xx	х	XX	х	XX	х	XX	х	xx
	Mild																				
	Moderate																				
	Severe																				
	Not Reported																				
Arthralgia	None																				
	Mild																				
	Moderate																				
	Severe																				
	Not Reported																				
Fever	None																				
	Mild																				
	Moderate																				
	Severe																				
	Not Reported																				
Feverishness	None																				
	Mild																				
	Moderate																				
	Severe																				

		Pre-	Dose	Post	-Dose	Da	ıy 1	Da	ny 2	Da	iy 3	Da	y 4	Da	y 5	Da	iy 6	Da	y 7	Day	7 8 +
Symptom	Severity	n	%	n	%	n	%	n	%	n	%	n	%	n	%	n	%	n	%	n	%
	Not Reported																				
Fatigue	None																				
	Mild																				
	Moderate																				
	Severe																				
	Not Reported																				
Headache	None																				
	Mild																				
	Moderate																				
	Severe																				
	Not Reported																				
Malaise	None																				
	Mild																				
	Moderate																				
	Severe																				
	Not Reported																				
Myalgia	None																				
	Mild																				
	Moderate																				
	Severe																				
	Not Reported																				
Nausea	None																				
	Mild																				
	Moderate																				
	Severe																				

		Pre-	Dose	Post	-Dose	Da	ıy 1	Da	ny 2	Da	iy 3	Da	y 4	Da	y 5	Da	ıy 6	Da	ny 7	Day	7 8 +
Symptom	Severity	n	%	n	%	n	%	n	%	n	%	n	%	n	%	n	%	n	%	n	%
	Not Reported																				
Vomiting	None																				
	Mild																				
	Moderate																				
	Severe																				
	Not Reported																				
Local Symptoms																					
Any Local Symptom	None	х	XX	х	XX	х	XX	х	XX	х	XX	х	xx	х	xx	х	XX	х	XX	х	xx
	Mild																				
	Moderate																				
	Severe																				
	Not Reported																				
Ecchymosis Severity	None																				
	Mild																				
	Moderate																				
	Severe																				
	Not Reported																				
Ecchymosis	None																				
	Mild																				
	Moderate																				
	Severe																				
	Not Reported																				
Erythema Measurement	None																				
	Mild																				
	Moderate																				

		Pre-	Dose	Post	-Dose	Da	ıy 1	Da	ny 2	Da	iy 3	Da	y 4	Da	y 5	Da	ıy 6	Da	ny 7	Day	7 8 +
Symptom	Severity	n	%	n	%	n	%	n	%	n	%	n	%	n	%	n	%	n	%	n	%
	Severe																				
	Not Reported																				
Induration/Swelling Severity	None																				
	Mild																				
	Moderate																				
	Severe																				
	Not Reported																				
Induration/Swelling Measurement	None																				
	Mild																				
	Moderate																				
	Severe																				
	Not Reported																				
Pain	None																				
	Mild																				
	Moderate																				
	Severe																				
	Not Reported																				
Pruritus	None																				
	Mild																				
	Moderate																				
	Severe																				
	Not Reported																				
Tenderness	None																				
	Mild																				
	Moderate																				

		Pre-	Dose	Post-	Dose	Da	y 1	Da	ny 2	Da	y 3	Da	y 4	Da	y 5	Da	y 6	Da	у 7	Day	8+
Symptom	Severity	n	%	n	%	n	%	n	%	n	%	n	%	n	%	n	%	n	%	n	%
	Severe																				
	Not Reported																				

Note: N = Number of subjects in the Safety Population who received the specified dose. Severity is the maximum severity reported post dosing for each subject for each day.

Tables with similar format:

- Table 30:Number and Percentage of Subjects Experiencing Solicited Events by Symptom, Severity, Dose, Day Post Dosing, and Treatment
Group Placebo, Post Dose 1
- Table 31:Number and Percentage of Subjects Experiencing Solicited Events by Symptom, Severity, Dose, Day Post Dosing, and Treatment
Group HEV-239, Post Dose 2
- Table 32:Number and Percentage of Subjects Experiencing Solicited Events by Symptom, Severity, Dose, Day Post Dosing, and Treatment
Group Placebo, Post Dose 2
- Table 33:Number and Percentage of Subjects Experiencing Solicited Events by Symptom, Severity, Dose, Day Post Dosing, and Treatment
Group HEV-239, Post Dose 3
- Table 34:Number and Percentage of Subjects Experiencing Solicited Events by Symptom, Severity, Dose, Day Post Dosing, and Treatment
Group Placebo, Post Dose 3
- Table 35:Number and Percentage of Subjects Experiencing Solicited Events by Symptom, Severity, Dose, Day Post Dosing, and Treatment
Group HEV-239, Post Any Dose
- Table 36:Number and Percentage of Subjects Experiencing Solicited Events by Symptom, Severity, Dose, Day Post Dosing, and Treatment
Group Placebo, Post Any Dose

Fable 37:	Number and Percentage	of Subjects E	Experiencing Solici	ted Events for Dose 1	l Compared with	Dose 3 by Treatment Gr	roup
-----------	-----------------------	---------------	----------------------------	-----------------------	-----------------	------------------------	------

Treatment Group		Dose 3 – Subjects with No Symptoms	Dose 3 – Subjects with Mild or Greater Symptoms	Dose 3 – Total Number of Subjects
Systemic Symptom	· · ·			
HEV-239	Dose 1 Subject with No Symptoms	x (%)	x (%)	x (%)
	Dose 1 Subjects with Mild or Greater Symptoms	x (%)	x (%)	x (%)
	Dose 1 Total Number of Subjects	x (%)	x (%)	x (100%)
Placebo	Dose 1 Subject with No Symptoms			
	Dose 1 Subjects with Mild or Greater Symptoms			
	Dose 1 Total Number of Subjects			
Local Symptoms	· · · ·			
HEV-239	Dose 1 Subjects with No Symptoms	x (%)	x (%)	x (%)
	Dose 1 Subjects with Mild or Greater Symptoms	x (%)	x (%)	x (%)
	Dose 1 Total Number of Subjects	x (%)	x (%)	x (100%)
Placebo	Dose 1 Subjects with No Symptoms			
	Dose 1 Subjects with Mild or Greater Symptoms			
	Dose 1 Total Number of Subjects			

Note: Denominators for percentages are the number of subjects in the Safety Population who received all three doses. [x] subjects did not get the second or third dose and are not included in this table.

		Post-D	ose 1 Sympt	om Duratio	n		Post-I	Dose 2 Symp	tom Durati	on		Post-E	Oose 3 Sympt	om Duratio	n
Symptom	n	Mean	Standard Deviation	Median	Min, Max	n	Mean	Standard Deviation	Median	Min, Max	n	Mean	Standard Deviation	Median	Min, Max
Any Symptom	xx	X.X	x.x	X.X	x, x	xx	X.X	X.X	X.X	x, x	xx	X.X	X.X	X.X	x, x
Systemic Symptoms															
Any Systemic Symptom	xx	X.X	x.x	X.X	х, х	xx	X.X	X.X	X.X	x, x	xx	X.X	X.X	x.x	x, x
Arthralgia															
Fever															
Feverishness															
Fatigue															
Headache															
Malaise															
Myalgia															
Nausea															
Vomiting															
Local Symptoms															
Any Local Symptom	xx	x.x	x.x	x.x	x, x	xx	X.X	x.x	X.X	x, x	xx	X.X	x.x	x.x	x, x
Ecchymosis Severity															
Ecchymosis															
Erythema Measurement															
Induration/Swelling Severity															
Induration/Swelling Measurement															
Pruritus															
Tenderness															

Table 38: Duration of Symptoms Among Subjects Experiencing Solicited Events

Note: n = Number of subjects in the Safety Population who received the specified dose and experienced the specified solicited symptom.

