- Phase III safety data was obtained from 56,302 subjects who received HEV-239 30 µg dose at 0, 1, and 6 months and a similar placebo group (hepatitis B vaccine)^{21,24} who were followed up to 4.5 years.²⁵ The population was 16-65 years of age predominantly female (56.5%) and Asian. Most of the adverse events were Grade 1 adverse events that generally resolved spontaneously without special treatment. Overall, vaccine was well tolerated with similar systemic AEs (20.3% versus 19.8%) to placebo. The most common systemic events included fever (18.6% vs 18.0%), fatigue and asthenia (2.1% versus 1.5%), and headache (1.1% versus 0.6%) in vaccine versus placebo. Higher rates of local adverse events were observed with vaccine versus placebo (13.5% versus 7.1%) although ≥Grade 3 events were similar. These local reactions were primarily increased pain (10.3 versus 5.5%) and swelling (2.3% versus 0.6%) in comparison to placebo. Unsolicited AEs (12% versus 11.9%), SAEs within 30 days of any dose (0.4% versus 0.4%), SAEs after the 30 day window periods (2.5% versus 2.5%), and deaths (0.2% versus 0.2%, none were considered related) were similar between vaccine and placebo recipients respectively. SAEs that were reported in the Phase 3 study were considered unrelated to study vaccine by the Data Safety Monitoring Board (DSMB).
- Retrospective data about women that became pregnant during the Phase III vaccine trial have been published.^{21,26} 37 pregnant women in the vaccine group received 53 doses of vaccine versus 31 pregnant women in the placebo group receiving 46 doses of placebo. The rates of adverse reactions were similar between the two groups and no SAEs reported. Importantly, fetal outcomes (rates of prematurity, body length, and weight) were similar in HEV-239 and placebo recipients suggesting the vaccine is safe for both the mother and fetus.
- Data have also been published regarding the safety of HEV-239 vaccination in hepatitis B surface antigen carriers.^{21,27} Local and systemic AEs overall and those ≥Grade 3 were similar in vaccine recipients and those that received placebo.

Post-Licensure Data:

After the vaccine was launched in China in October 2012,²⁸ Innovax implemented a series of post-marketing clinical studies but data are limited. A post-marketing surveillance database supports the safety of the vaccine based upon an estimated >279,000 administrations of HEV-

DMID/NIAID/NIH

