3.3. Study Definitions and Derived Variables

The baseline value will be defined as the last value obtained prior to the first vaccination/dose of study product.

Seronegative samples will be defined as per the Wantai HEV-IgM and IgG ELISA package inserts (Absorbance Value / Cut-Off Value (A/C.O.) <0.9).

Seroconversion will be defined as a change from a seronegative result to a seropositive result as defined by the Wantai HEV-IgM and IgG ELISA package inserts (A/C.O. >1.1). Samples with borderline A/C.O. values (0.9-1.1) will be retested in duplicate. If both retests are negative (as defined above), the result will be reported as negative. If one or both retests are positive, the result will be reported as positive. If both retest values are in the borderline zone, the result will be reported as indeterminant.

A 4-fold seroconversion will be defined as a HEV IgG ≥ 0.154 in a subject that was HEV seronegative at baseline.

Duration of solicited events will be defined as the number of contiguous symptomatic days.

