6.8. Multiple Comparisons/Multiplicity

This study was not designed to test any specific null hypothesis, and as such no adjustments for multiple testing are planned.

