9.3.1. Solicited Events and Symptoms

Systemic solicited adverse events were collected pre-vaccination, and systemic and local solicited adverse events were collected 30 minutes post-vaccination and then daily for 7 days after each vaccination and graded on a scale of 0 (absent), 1 (mild), 2 (moderate) and 3 (severe). The grading scales are presented in Table 4 and Table 5. Systemic events include: arthralgia, fever, feverishness, fatigue, headache, malaise, myalgia, nausea, and vomiting. Local events include: ecchymosis severity and measurement, erythema measurement, induration/swelling severity and measurement, pain, pruritus, and tenderness.

The proportion of subjects reporting at least one solicited adverse event will be summarized for each solicited adverse event, any systemic symptom, any local symptom, and any symptoms. The 95% confidence interval (CI) calculated using Clopper-Pearson methodology from a binomial distribution (SAS Proc Freq with a binomial option) will be presented (Table 27).

For each systemic and local event, any systemic event, any local event, and any solicited event, the maximum severity over 7 days after each vaccination will be summarized for the Safety population. The number and percentage of subjects reporting each event will be summarized by the maximum severity and treatment group, separately for each vaccination and over all vaccinations. For each event the denominator is the number of subjects with non-missing data for the specific event (Table 28).

The number of subjects reporting a solicited adverse event will be summarized for each day post vaccination for each vaccination and for all vaccinations combined both in a summary table (Table 29, Table 30, Table 31, Table 32, Table 33, Table 34, Table 35, and Table 36) and graphically in a bar chart (Figure 11, Figure 12, Figure 13, Figure 14, Figure 15, Figure 16, Figure 17, and Figure 18). A comparison of the event rate for each treatment group between vaccination 1 and vaccination 3 will be presented (Table 37). The duration of solicited adverse events will be summarized by dose number and treatment group (Table 38).

Solicited adverse events by subject will be presented in Listing 8 and Listing 9.

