12.2.2 Displays of Adverse Events

Table 4: Solicited Adverse Event Grading Scale – Local (Injection Site) Reactogenicity Grading

Local (Injection Site) Reaction	Mild (Grade 1)	Moderate (Grade 2)	Severe (Grade 3)
Pain – experienced without touching the injection site (spontaneous discomfort)	No pain medication or it requires use of a non-narcotic pain reliever ≤24hours OR does not interfere with activity	Repeated use of non-narcotic pain reliever >24 hours OR interferes with activity	Any use of narcotic pain reliever OR prevents daily activity
Tenderness – hurts only when injection site is touched or the arm is moved	Discomfort only to touch	Discomfort with movement	Significant discomfort at rest
Pruritus (Itching)	Does not interfere with daily activity	Interferes with daily activity	Prevents daily activity
Ecchymosis (Bruising) Severity ^a	Does not interfere with daily activity	Interferes with daily activity	Prevents daily activity
Induration (Hardness)/Swelling Severity ^a	Does not interfere with daily activity	Interferes with daily activity	Prevents daily activity
Ecchymosis (Bruising) Measurement ^b	25mm – 50mm	51 mm – 100mm	>100 mm
Erythema (Redness) Measurement ^b	25 mm – 50 mm	51 mm – 100 mm	>100 mm
Induration (Hardness)/Swelling Measurement ^b	25 mm – 50 mm	51 mm – 100 mm OR interferes with activity	>100 mm OR prevents daily activity

^a Will also be measured in mm but size will not be used as halting criteria.

^b Will not be used as halting criteria.

Systemic	Mild (Grade 1)	Moderate (Grade 2)	Severe (Grade 3)
Feverishness (Chills/Shivering/Sweating)	No interference with daily activity	Some interference with daily activity	Significant interference, prevents daily activity
Fatigue (Tiredness)	No interference with daily activity	Some interference with daily activity	Significant interference, prevents daily activity
Malaise (General Unwell Feeling)	No interference with daily activity	Some interference with daily activity	Significant interference, prevents daily activity
Myalgia (Body Aches/Muscular Pain) ^a	No interference with daily activity	Some interference with daily activity	Significant interference, prevents daily activity
Arthralgia (Joint Pain) ^a	No interference with daily activity	Some interference with daily activity	Significant interference, prevents daily activity

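### The Table 38 shell for duration of solicited symptoms has no Pain row, although SAP 9.3.1 lists pain as a solicited local event and assigns duration to that table

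*SAP*

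**What the plan says.** SAP 9.3.1 sets out the local items: "Local events include: ecchymosis severity and measurement, erythema measurement, induration/swelling severity and measurement, pain, pruritus, and tenderness". The same section then commits to a duration summary: "The duration of solicited adverse events will be summarized by dose number and treatment group (Table 38"). SAP 3.3 says how duration is counted, with no exception for any symptom: "Duration of solicited events will be defined as the number of contiguous symptomatic days".

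The Table 38 shell in SAP Appendix 1 is titled "Duration of Symptoms Among Subjects Experiencing Solicited Events". For each of the three doses it has columns for n, mean, standard deviation, median, and minimum and maximum. It has rows for any symptom, any systemic symptom, the nine systemic symptoms and any local symptom. Seven individual local rows follow, and pain is not among them. Neither the columns nor the title separate the treatment groups.

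SAP Table 4 grades pain as an item of its own, described as "Pain – experienced without touching the injection site (spontaneous discomfort"). Tenderness is a separate item in that table, felt on touch or on moving the arm.

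**The concern.** The text of the SAP and the drawing of the table disagree. A programmer who builds Table 38 from the shell would deliver a duration summary for itching, bruising, redness, swelling and tenderness but none for pain, and the report would fall short of what 9.3.1 promises.

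Pain is not a minor item for this vaccine. Protocol 2.3.1, describing the Phase III trial at this study's dose and schedule, names pain first among the local reactions that exceeded placebo. The Phase I summary in the same section mentions one subject whose swelling and pain were present on Day 7. Safety and reactogenicity after each dose is a primary objective of this trial. How long spontaneous injection-site pain lasts is something a reader of the clinical study report would expect to find tabulated.

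**Working it through.** The plan gives no figure to reproduce here. The check is a comparison of rows, followed by simple arithmetic on the reaction rates in the protocol.

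**Step 1. Local items, place by place**

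| Local item | SAP 9.3.1 text | Tables 27 and 28 | Table 29 | Table 38 |
|---|---|---|---|---|
| Ecchymosis, severity | yes | yes | yes | yes |
| Ecchymosis, measurement | yes | yes | yes (labelled Ecchymosis) | yes (labelled Ecchymosis) |
| Erythema, measurement | yes | yes | yes | yes |
| Induration/swelling, severity | yes | yes | yes | yes |
| Induration/swelling, measurement | yes | yes | yes | yes |
| Pain | yes | yes | yes | **no** |
| Pruritus | yes | yes | yes | yes |
| Tenderness | yes | yes | yes | yes |
| Count | 8 | 8 | 8 | 7 |

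Tables 30 to 36 follow the format of Table 29. In Tables 27, 28 and 29 pain sits between induration/swelling measurement and pruritus, which is where Table 38 skips. The other Table 38 rows are present and in order.

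**Step 2. Does another planned display give pain duration?**

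- Any Symptom and Any Local Symptom in Table 38 include pain days, but mixed with those of other symptoms.
- Tables 29 to 36 count subjects by severity on each day, ending in a pooled column for Day 8 onward. They do not link one subject's days together. Dividing summed daily counts by the number of subjects with pain gives at best an average number of pain days. It does not give the contiguous spell that SAP 3.3 defines, nor its median or range.
- Listing 9 shows local symptoms by subject, dose and post-dose day, so duration can be worked out there by hand. Its shell has no stop-date column.

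No planned summary therefore reports pain-specific duration.

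**Step 3. How prominent is pain in the protocol's own data?** (Protocol 2.3.1, vaccine against placebo)

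| Trial and reaction | Rates | Difference (points) | Ratio |
|---|---|---|---|
| Phase III, pain | 10.3% vs 5.5% | 10.3 − 5.5 = 4.8 | 10.3 / 5.5 = 1.87 |
| Phase III, swelling | 2.3% vs 0.6% | 2.3 − 0.6 = 1.7 | 2.3 / 0.6 = 3.83 |
| Phase II Group A (20 µg), itching | 6.0% vs 1.6% | 6.0 − 1.6 = 4.4 | 6.0 / 1.6 = 3.75 |
| Phase II Group A (20 µg), swelling | 4.3% vs 0.7% | 4.3 − 0.7 = 3.6 | 4.3 / 0.7 = 6.14 |
| Phase II all recipients, pain | 2.4% vs 0.2% | 2.4 − 0.2 = 2.2 | 2.4 / 0.2 = 12.0 |

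**Step 4. Would the row have anything in it?** This needs an assumed pain rate p per vaccinee. With 20 vaccinees the expected number with pain is 20p, and the chance of at least one is 1 − (1 − p)^20.

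- p = 10.3% (Phase III): 20 × 0.103 = 2.06 expected; 1 − 0.897^20 = 0.89.
- p = 2.4% (Phase II): 20 × 0.024 = 0.48 expected; 1 − 0.976^20 = 0.38.

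The row would probably be sparse, and it could be empty at the lower rate.

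**The case against.** The strongest reply is that Table 38 is a mock-up and the text of 9.3.1 governs. The planned analysis already covers pain, and harm arises only if the shell is followed literally. That is fair, but shells exist to be programmed from, and nothing in the SAP tells the programmer which of the two to follow.

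A second reply is that the information survives elsewhere. A reader might infer from the missing row that pain duration is lost. The documents do not support that: daily pain appears in Tables 29 to 36, and subject-level pain appears in Listing 9 for only 25 subjects. What is missing is the pain-specific summary line.

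A third reply is that duration is not an endpoint. The primary reactogenicity endpoint counts solicited events, and Tables 27 and 28, which report subjects with each event, both carry pain. SAP 6.8 adds: "This study was not designed to test any specific null hypothesis, and as such no adjustments for multiple testing are planned". This stands. The gap concerns a descriptive display that supports the primary objective, and no primary endpoint is omitted.

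A reader might also link the omission to the halting criteria, because Protocol 8.6.1 refers to severe injection-site events lasting 3 or more days. That link fails. The criteria operate during the trial, and Protocol section 11 provides real-time alerts for potential Grade 3 entries. Table 38 is produced after database lock and has no severity breakdown.

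**Conclusion.** The point holds as a mismatch between the SAP text and its shell: one of eight local items is missing from the table that 9.3.1 designates for duration. The tenderness row does not stand in for it. The consequence is a missing pain-specific duration summary. No estimate of incidence or severity, analysis population or sample-size figure changes.

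Two stronger readings should be resisted. One is that the sponsor chose to leave pain out. Neither 9.3.1 nor 3.3 makes such an exception, and the sibling shells point to an oversight. The other is that pain is the local reaction most in excess on every measure. It has the largest absolute excess in Phase III, but swelling has the larger ratio there (3.83 against 1.87). In Phase II, itching in Group A has the largest absolute excess of the reactions listed, although those Phase II comparisons use different recipient groups.

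The conclusion rests on two assumptions. The shell as read must be complete; a row lost in converting the PDF to text cannot be wholly excluded, although the rest of the table is intact. And the row labelled Ecchymosis must be the measurement row, as its position and the same label in Table 29 suggest.

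**What to change.** First check the source shell, to rule out a row lost in PDF conversion. If the row is absent there, add Pain to the local block of Table 38, between induration/swelling measurement and pruritus, with n, mean, standard deviation, median, minimum and maximum after each dose.

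Present the table by treatment group, as 9.3.1 states. A Pain row added to the present layout alone would still leave vaccine and placebo unseparated. Either a second set of columns or one table per arm, as in Tables 29 to 36, would do.

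The cost is one shell row and a layout change to one table. Protocol 7.1.4 already has subjects enter pain through Day 8 after each vaccination, so no new data are needed.
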